10.0 PARTICIPANT DISCONTINUATION, FOLLOW-UP

10.1 Treatment Discontinuation

Study medication is discontinued in the event of intolerable side effects, safety concerns preventing further medication treatment (i.e., pregnancy), relapse, or the end of the 24-week active treatment phase (see MOP). Participants discontinuing medication, but not yet meeting relapse criteria, prior to week 24 continue within the same study assessment schedule. Participants meeting relapse criteria discontinue medication and research visits. All participants who end treatment early (prior to week 21) are encouraged to attend a visit at week 24 and are seen in long-term follow-up (weeks 28 and 36). In all cases of treatment discontinuation, the research team makes an effort to arrange for continued community treatment, as appropriate and available, including further XR-NTX and BUP-NX, or methadone maintenance and intensive outpatient psychosocial aftercare. For participants receiving BUP-NX, who do not wish to continue, or for whom community resources are not available, the study will provide a two-week BUP-NX taper, if clinically appropriate.

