11.3.2 Medical Management

A Medical Management attendance log is completed to document attendance or non-attendance at each Medical Management session during the active treatment phase. The Medical Management discontinuation form is completed when MM visits end (at week 24 post-randomization, when the primary outcome of opioid relapse is met, or for other reasons as determined by the study clinician).

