Phase 3: Active Treatment (Week 1 through Week 24): Following randomization, participants will be inducted as soon as practicable and treated per their assigned active medication condition and followed as outpatients until 24 weeks post-randomization. Assessment visits will occur weekly. Participants whose induction onto their assigned study medication is delayed will also attend weekly research visits. Medical management visits will initially occur weekly, transition to every two weeks and then to every four weeks. In order to retain participants in treatment, and consistent with good practice, we permit flexibility with dosing. The window for Visit 1 is -3/+6 days to accommodate induction; however, induction may occur after Visit 1. A +/- 3-day window will be permissible for subsequent weekly visits. For participants who relapse and/or become lost to follow up, a -3/+28 day window is permissible to complete the EOT visit. Participants who relapse will discontinue study medication and weekly research visits, but should be encouraged to attend the week 24 and follow up visits at weeks 28 and 36.

Phase 4: Post Treatment Follow-up (Week 25 through Week 36): Toward the end of the 24-week treatment period, participants will be referred for follow-up care in the community (which could include continuation of medication, if available, indicated, and desired), and follow-up outcomes will be assessed at week 28 and week 36 post-randomization. For participants receiving BUP-NX, who do not wish to continue, or for whom community resources are not available, the study will provide a two-week BUP-NX taper (beginning at the week 24 visit). A -3/+28 day window will be permissible for the scheduled week 28 visit and a +/- 4 week window will be permissible for the scheduled week 36 visit.

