7.4.1 Adverse Events (AEs) and Serious Adverse Events (SAEs)

At each medical management visit the study clinician will assess for AEs and SAEs by asking the study participant, "How have you been feeling since your last visit?" AEs and SAEs may also be spontaneously reported to study staff at any visit following consent. AEs and SAEs suggesting medical or psychiatric deterioration will be brought to the attention of a study clinician for further evaluation and management. Medical management visits will emphasize overdose risk and risk-management; any reported overdose will be recorded as an AE or SAE. AE and SAE reporting will be according to the reporting definitions and procedures outlined in the protocol and in accordance with applicable regulatory requirements.

For the purpose of this study, the following AE will not require reporting in the data system but will be captured in the source documentation as medically indicated:

- Grade 1 (mild) unrelated adverse events

This would typically include mild physical events such as headache, cold, etc., that were considered not reasonably associated with the use of the study drug/intervention.

Events related to the injection of the study medication will be recorded on the Injection Site Abnormality (INA) form and will not be duplicate-reported on an AE form (See Section 7.4 for details on Injection Site examination summaries). Events related to withdrawal symptoms will be captured on the SOWS and HAM-D and will not be duplicate-reported on an AE form. Withdrawal symptoms not captured by the SOWS or HAM-D should be reported as an AE. Events captured on study specific forms (INA, SOWS, HAM-D) will not be recorded separately as an AE, unless they meet the SAE definition. Any of these events that meet the definition of an SAE will be reported on the AE/SAE form set. Any spontaneous reporting of withdrawal symptoms by the participant will be captured on AE form in the following situations: withdrawal symptoms reported at visits without scheduled specific structured questionnaires (SOWS, HAM-D); and withdrawal symptoms not listed in the specific structured questionnaires (SOWS, HAM-D) reported at any visit.

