Adverse events (AEs), including serious adverse events (SAEs), will be summarized by body system and preferred term using MedDRA (The Medical Dictionary for Regulatory Activities) version 19.0 or higher. Adverse events will be presented in two ways: (1) the number and proportion of participants experiencing at least one incidence of each event will be presented overall and by treatment group. The incidence of adverse events and serious adverse events by

type will be compared between treatment arms using either Fisher's Exact mid-p-value or Chi-Square analysis as appropriate; and (2) a table displaying the total number of each event will be given overall and by treatment group. Listings of serious adverse events will be given, sorted by treatment, body system and preferred term. Detail in these listings will include severity, relationship to study drug, and action taken as available.

Treatment emergent AEs are defined as AEs occurring after participants have been inducted on study medication. Induction is defined as having had an injection if in the XR-NTX arm or having been dispensed medication if in the BUP-NX arm.

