MA Avery Road							
SW Turquoise Lodge Hospital							
OV Maryhaven							
FL Gateway Community Services							
PA Tarzana Treatment Centers							
NEC Stanley Street Treatment and Resources (SSTAR)							
GNY Bellevue Hospital Center							
PNW ETS/RCKC							
MA Avery Road							
SW Turquoise Lodge Hospital							

[figure not shown]
Refer to figures for details regarding the color-coding.

Table 43: Summary of Participants with Responses Indicating Potential Suicidality by Treatment Arm			
	BUP-NX (N=)	XR-NTX (N=)	Total (N=)
Number of Participants who endorsed suicidal ideation on CHRT at Screening			
Number of Participants who endorsed suicidal ideation on CHRT at any Follow-up Visit			
Number of Participants who endorsed suicidal ideation ¹ on HAM-D ¹ at Screening			
Number of Participants who endorsed suicidal ideation on HAM-D at any Follow-up Visit			
Number of Participants who ever endorsed a suicide attempt ² on the HAM-D at any Follow-up Visit			
Number of Participants with AE's MedDRA-coded as either Suicide attempt, Suicidal Ideation, Self injurious behavior or Depression suicidal			

¹ Indicated as a response of 1 or higher to the HAM-D Suicide Question.

[figure not shown]
² Indicated as a response of 4 on the HAM-D Suicide Question

Figure 18: Participant-level Plot of HAM-D Question 3: Suicide by Treatment Arm
Figure 18A: Treatment Arm = BUP-NX

Example figure provided. The figure colors will be modified to accommodate color blind readers.

Figure 18B: Treatment Arm = XR-NTX

Example figure provided. The figure colors will be modified to accommodate color blind readers.

Figure 21: Participant-level Plot of CHRT Question 16: I have a plan to kill myself, by Treatment Arm

Figure 12A: Treatment Arm = BUP-NX

[figure not shown]
Example figure provided. The figure colors will be modified to accommodate color blind readers.

Figure 12B: Treatment Arm = XR-NTX

[figure not shown]
Example figure provided. The figure colors will be modified to accommodate color blind readers.

Figure 22: Participant-level Trajectories for Participants with Aspartate Aminotransferase > 225 IU/L by Treatment Arm

Example figure provided.

Figure 23: Participant-level Trajectories for Participants with Alanine Aminotransferase > 225 IU/L by Treatment Arm

Example figure provided.

Table 44: Listing of Liver Function Tests for ALT and AST exceeding 45 IU/L by Treatment Arm							
Treatment Arm=BUP-NX							

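### AE and SAE incidence is compared between arms only as crude proportions and counts, although frequent AE questioning ends at relapse, the endpoint that may itself differ by arm

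*SAP*

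**What the plan says.** **Analysis.** SAP 7.4.1 states that "the number and proportion of participants experiencing at least one incidence of each event will be presented overall and by treatment group". Incidence by "type will be compared between treatment arms using either Fisher's Exact mid-p-value or Chi-Square analysis as appropriate". A second table gives the total number of each event. Neither 7.4.1 nor shells 33 to 36 in SAP Appendix A contain person-time, a time-to-event analysis or a common observation window. Treatment-emergent status starts at induction and has no stated end.

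**Elicitation.** SAP 7.4.1: "At each medical management visit the study clinician will assess for AEs and SAEs by asking the study participant" how they have felt since the last visit. Spontaneous reports are accepted at any visit. The CHRT-SR (SAP 7.2) is given at screening, induction, MM visits and weeks 28 and 36.

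**What ends at relapse.** Protocol 10.1: "Participants meeting relapse criteria discontinue medication and research visits". Protocol 11.3.2 closes MM visits at week 24, "when the primary outcome of opioid relapse is met", or for other reasons the clinician determines.

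**What remains.** SAP 1.2: "Participants who relapse will discontinue study medication and weekly research visits, but should be encouraged to attend the week 24 and follow up visits". The two follow-up contacts fall in weeks 28 and 36, and Protocol 10.2 adds active outreach for them.

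**Suicidality.** Table shell 43 has rows such as "Number of Participants who endorsed suicidal ideation on CHRT at any Follow-up Visit". These are counts by arm, and no test is specified.

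**The concern.** The safety hypothesis in SAP 2.2 is about equivalent rates of AEs and SAEs. A proportion with at least one event estimates a comparable risk only if both arms are watched for similar time with similar intensity. Here intensive watching ends at the primary endpoint, which the trial is powered to find different between arms. SAP 3.2 also anticipates that induction failure on XR-NTX may lead to relapse.

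A difference in crude incidence could therefore reflect how long participants were asked, and a null could hide a real difference. The thinnest surveillance falls after relapse and the end of medication. That period matters to Protocol 5.2, which names overdose through the 3-month follow-up, and to Protocol 10.2, which gives post-treatment overdose as a reason for follow-up.

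**Working it through.** **1. Reproduce the planning figure.** The only arm-specific relapse rates are in SAP 3.3, Table 2: 40% relapse-free in one arm, hazard ratio .633 or .678, 200 per arm, two-sided 5%.
- HR .633: 0.40^.633 = 56.0% relapse-free. Relapses = 200 × 0.60 + 200 × 0.44 = 208. Power = Φ(√208 × |ln .633|/2 − 1.96) = 91.0% (plan: 90%).
- HR .678: 53.7% relapse-free (plan: 53.8%), 212.5 relapses, power 80.9% (plan: 80%).

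Both agree, so these rates are used below.

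**2. Frequently monitored time.** Weekly relapse hazard λ = −ln(S)/24: 0.03818 for S = 40%, 0.02583 for 53.8%, 0.02416 for 56%. SAP 5.3.2 back-dates relapse to the start of the qualifying period, but visits stop only when criteria are met. So a delay d of 0 or 4 weeks (four use weeks) is tried. Mean weeks = d + (1 − exp(−λ(24 − d)))/λ.

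| d | 40% arm | 53.8% arm | 56% arm | ratio |
|---|---|---|---|---|
| 0 | 15.7 | 17.9 | 18.2 | 0.88 to 0.86 |
| 4 | 18.0 | 19.6 | 19.9 | 0.92 to 0.91 |

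The higher-relapse arm has about 8 to 14% less. Expected MM visits on the Protocol 8.5 schedule, with no relapse before week 3, are 9.7 against 10.6 to 10.7 (d = 0) or 10.7 against 11.3 to 11.4 (d = 4).

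**3. Effect on the crude proportion.** Assume the same constant AE hazard h in both arms. For 30% true 24-week risk, h = −ln(0.70)/24 = 0.01486. With d = 0 and nothing seen after relapse, P(seen) = h/(h + λ) × (1 − exp(−24(h + λ))):
- 40% arm: 0.2802 × (1 − 0.40 × 0.70) = 20.2%
- 53.8% arm: 0.3652 × (1 − 0.538 × 0.70) = 22.8%
- 56% arm: 0.3808 × (1 − 0.56 × 0.70) = 23.2%

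With d = 4 the figures are 23.0% against 24.9 to 25.2%.

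**4. False rejection.** Pooled two-proportion test, two-sided 5%, 300 per arm (the projected total of about 600). Recovery is the share of missed events picked up at later contacts.

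| True risk | d | none recovered | half | all |
|---|---|---|---|---|
| 30% | 0 | 12.1 to 14.4% | 6.5 to 7.0% | 5% |
| 30% | 4 | 8.5 to 9.6% | 5.8 to 6.0% | 5% |
| 5% | 0 | 6.0 to 6.4% | 5.2 to 5.3% | 5% |
| 5% | 4 | 5.5 to 5.7% | 5.1 to 5.2% | 5% |

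**5. Direction.** Take a 5% event, 40% against 53.8% relapse-free, d = 0. If relapse doubles the event hazard, the crude ratio (higher-relapse arm over the other) is 1.00 with half of post-relapse events recovered and 1.05 with 80% recovered. If relapse triples it, the ratios are 1.04 and 1.09. The sign depends on quantities that the documents do not give.

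**The case against.** The strongest reply is that questioning does not stop at relapse. Relapsers have an EOT visit, are encouraged to attend week 24 and are followed at weeks 28 and 36 with outreach. Protocol Appendix B has AEs assessed at every clinic visit. The AE question reaches back to the previous visit, so a later contact can fill the gap, and the NMS form records hospital and emergency use. This stands: what ends is frequent questioning. It does not remove the point, because week 24 is only encouraged, recall may span months, and the appendices disagree on when AE assessment ends. Appendix A says 30 days after the last study visit; Appendix B says 30 days after the last active treatment visit.

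A reader might also infer that the arm with more relapse will look safer. That needs a hazard that does not rise after relapse and little later recovery; step 5 shows it can reverse. A reader might infer that the suicidality scales are tested in the same way. They are not: only suicidality coded as an AE falls under the 7.4.1 test.

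Two limits on the size also stand. Shells 33 to 36 cover treatment-emergent events in inducted participants, whereas the calculation takes all 300 per arm as inducted at day 0. If induction failure drives much of the relapse difference, the difference among inducted participants may be smaller. And mild unrelated events, injection-site events and symptoms captured on the SOWS or HAM-D are mostly kept off the AE form, so few single AE types may reach 30%.

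Finally, one constant-rate model would not be a neutral replacement. SAP 2.2 expects some symptoms in the 1 to 4 weeks after naltrexone initiation, so dividing by longer follow-up would favour the arm that stays longer.

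**Conclusion.** The point holds in a limited form. The plan compares AE and SAE incidence with no allowance for surveillance that may differ by arm, and the quantity tested is not the rate that the hypothesis names. At the planning relapse rates the shortfall in frequently monitored time is about 8 to 14%. False rejection is modest for common events (8.5 to 14.4% at 30% risk with no recovery, 5.8 to 7.0% with half recovered), slight for rare ones, and absent with full recovery.

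These figures assume exponential relapse, equal constant AE hazards, 300 per arm inducted at day 0, and illustrative risks and recovery shares that are not in the documents. They do not show which arm would be favoured, and for overdose and suicidality the documents leave that open. The case for change is that the present tables cannot separate differential risk from differential surveillance. Shells 4 and 11 help only partly: they give visit completion and drug exposure, not AE surveillance time.

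**What to change.** Keep the crude proportions and their tests, and add to SAP 7.4.1:

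- **Time to first event** by arm, with a stated start (randomization or induction) and censoring rule.
- **Events per person-week of AE surveillance**, by Poisson or negative binomial regression with a log person-time offset, reported by period (for example the first 4 weeks and later) so that a constant hazard is not assumed.
- **Person-weeks and number of AE and CHRT assessments by arm** in Tables 33 to 36 and 43.
- **Overdose and SAEs split into before and after relapse**, through week 36, stating whether the split uses the back-dated onset or the date criteria were met.

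Reconcile Protocol Appendices A and B on the end of AE assessment, state that end in 7.4.1, and say whether the table denominators are randomized or inducted participants.

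The cost is SAP wording and table programming. Visit, relapse and AE onset dates are already collected, and trial conduct does not change. The rate results will depend on the chosen definition of surveillance time, and censoring at relapse may be informative; the SAP should say so.
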